12.1.3 Analysis of the secondary endpoints

The positive and negative predictive values are reported descriptively with 95%-logit confidence intervals. Their calculation follows from the analysis method chosen for the primary endpoints. To estimate predictive

values with the mixed binary logistic regression model, the true disease status represents the dependent variable. The test results are included as fixed effects and again a random-intercept is estimated for each centre. Positive predictive value is estimated via the calculation of the marginal mean for a test positive result. False-negative rate, which is the counter probability of the negative predictive value, is estimated via the calculation of the marginal mean for a non-diseased individual. Two-sided 95%-logit confidence intervals with pvalues are reported.

Other secondary endpoints, including safety endpoints, will be analysed descriptively.

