In the first pair of primary hypotheses, sensitivity and specificity are considered as co-primary endpoints. They are combined via the Intersection-Union Test. The global null hypothesis can only be rejected if both individual null hypotheses of sensitivity and specificity are rejected. The corresponding first global alternative hypothesis states that the IP exceeds a pre-defined minimum sensitivity of 80% and specificity of 65%. The second primary global hypothesis considers the three-level decision system. Due to the hierarchical order of primary hypotheses, the second primary global hypothesis can only be evaluated in a confirmative way if the first global primary hypothesis leads to a significant result. The analysis of the first global primary hypothesis contains the estimation of the resulting sensitivity and specificity of the IP according to the defined cut-off value of 12 mmHg. For the estimation, a mixed binary logistic regression model is used [26]: The binary test result represents the dependent variable, the true disease status is included as fixed effect. Additionally, a random-intercept is estimated for each centre. Sensitivity is estimated via the calculation of the marginal mean for a diseased individual (=surgical intervention performed which confirmed post-operative hemorrhage needing intervention). False-positive rate, which is the counter probability of the specificity, is estimated via the calculation of the marginal mean for a non-diseased individual. Two-sided 95%-logit confidence intervals with p-values are reported. The positive and negative predictive values are reported descriptively with 95%-logit confidence intervals. Their calculation follows from the analysis method chosen for the primary endpoints. To estimate predictive values with the mixed binary logistic regression model, the true disease status represents the dependent variable. The test results are included as fixed effects and again a random-intercept is estimated for each centre. Positive predictive value is estimated via the calculation of the marginal mean for a test positive result. False-negative rate, which is the counter probability of the negative predictive value, is estimated via the calculation of the marginal mean for a nondiseased individual. Two-sided 95%-logit confidence intervals with p-values are reported.

Other secondary endpoints, including safety endpoints, will be analysed descriptively.

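### The protocol's estimator for the negative predictive value conditions on disease status instead of a negative test, and so cannot be computed from the model it names

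*Protocol*

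**What the plan says.** Protocol section 4.2 lists the positive and negative predictive values as secondary endpoint EP5. Section 12.1.3 gives the estimators in four steps:

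- Outcome of the model: "values with the mixed binary logistic regression model, the true disease status represents the dependent variable".
- Predictors: "The test results are included as fixed effects and again a random-intercept is estimated for each centre".
- PPV: "Positive predictive value is estimated via the calculation of the marginal mean for a test positive result".
- NPV, through its complement, which the protocol calls the false-negative rate: "counter probability of the negative predictive value, is estimated via the calculation of the marginal mean for a non-diseased individual".

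The statistical considerations in the synopsis (section 1) carry the same NPV sentence: "counter probability of the negative predictive value, is estimated via the calculation of the marginal mean for a nondiseased individual".

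Section 12.1.2 sets up the primary model the other way round, with the test result as outcome and disease status as fixed effect. There the false-positive rate is "estimated via the calculation of the marginal mean for a non-diseased individual", which is correct for that model.

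Section 12.1.3 says that predictive values are reported descriptively, yet also calls for p-values. It gives no null value for either of them.

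**The concern.** The complement of the NPV is the probability of disease given a negative test. The sentence has two faults.

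1. **Wrong conditioning.** It asks for a marginal mean at a level of disease status. In the model just named, disease status is the outcome and only the test result (plus centre) is on the right-hand side. A marginal mean can be taken at test positive or at test negative, but not at non-diseased.
2. **Wrong label.** The false-negative rate is the probability of a negative test given disease, that is 1 - sensitivity. The complement of the NPV is the false omission rate.

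At stake is the NPV half of EP5. Section 12.2 asks for consecutive recruitment without selection so that the predictive values are valid, so the protocol does mean these figures to be used. A programmer who follows the text has no quantity to extract, or may look for the one model in which the phrase has a meaning and extract the wrong one.

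**Working it through.** **Inputs.** Section 12.2: sensitivity 99%, specificity 95%, prevalence 1.5%, minimum sensitivity 80%, minimum specificity 65%, N = 1,470. Section 3.1: reported bleeding rates of 0.6% to 4%, used here as a range for prevalence. The test is treated as binary, as under the 12 mmHg cut-off. The centre effect is left out of the arithmetic.

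**The plan's own figure.** The protocol gives no planning value for the NPV. Its event count reproduces: 1,470 x 0.015 = 22.05, against 22 stated.

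**Step 1: cell probabilities at the planning values.**

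| | Test positive | Test negative |
|---|---|---|
| Diseased | 0.015 x 0.99 = 0.01485 | 0.015 x 0.01 = 0.00015 |
| Non-diseased | 0.985 x 0.05 = 0.04925 | 0.985 x 0.95 = 0.93575 |

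**Step 2: the model named in section 12.1.3 (disease on test).**

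- Mean at test positive: 0.01485 / (0.01485 + 0.04925) = 0.2317. This is the PPV.
- Mean at test negative: 0.00015 / (0.00015 + 0.93575) = 0.00016. This is 1 - NPV, so NPV = 99.98%.
- Mean at non-diseased: not defined, because disease is the outcome. Conditioning on the outcome anyway gives a trivial 0.

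**Step 3: the primary model of section 12.1.2 (test on disease).**

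- Mean at diseased: 0.99, the sensitivity.
- Mean at non-diseased: 0.05, which is 1 - specificity.

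Logistic fits in both directions to the expected two-by-two table, without the centre effect, return these same values.

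**Step 4: the candidate readings of the NPV sentence.**

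| Reading | Value for 1 - NPV | Implied NPV |
|---|---|---|
| Named model, test negative (correct) | 0.00016 | 99.98% |
| Named model, non-diseased (as written) | none | none |
| Primary model, non-diseased | 0.05 | 95% |
| Taken from the label (1 - sensitivity) | 0.01 | 99% |

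**Step 5: range.** With sensitivity and specificity held at 99% and 95%:

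- Prevalence 0.6%: 1 - NPV = 0.00006 / (0.00006 + 0.9443) = 0.00006, so NPV = 99.99%.
- Prevalence 4%: 1 - NPV = 0.0004 / (0.0004 + 0.912) = 0.00044, so NPV = 99.96%.

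The primary-model reading gives 95% at every prevalence, which no predictive value should do. At the minimum thresholds and prevalence 1.5%, the correct 1 - NPV is 0.003 / (0.003 + 0.64025) = 0.0047, an NPV of 99.53%. The primary-model reading gives 65%.

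**The case against.** The best defence is that the intent is plain. The paragraph names the target as the complement of the NPV, sets up the right model and takes the PPV at the right predictor level. The faulty phrase matches the false-positive-rate sentence in section 12.1.2 and looks carried over from it. A competent statistician would read it as test negative. This stands, and it limits the weight of the point. It does not remove it: the protocol states an estimator in two places, and states it wrongly in both. A SAP with the correct rule would depart from the protocol, and one that copied the protocol would inherit the error.

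Three stronger readings are tempting, and the documents do not support them.

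- **That the plan will report an NPV of 95%.** This requires leaving the model that section 12.1.3 names and returning to that of section 12.1.2. In the named model there is simply no such quantity. An NPV equal to the reported specificity would also be conspicuous.
- **That the trial's safety conclusion is affected.** Safety is EP3, assessed through adverse events. The remark in section 12.2 that false negatives matter more to the patient justifies the higher sensitivity threshold and does not concern this figure.
- **That the logit interval for the NPV will usually fail because no test-negative patient bleeds.** With 22 events and no missing readings the chance of an empty cell is 0.99^22 = 80% at sensitivity 99%, but 0.95^22 = 32% at 95% and 0.90^22 = 10% at 90%. Section 12.1.2 also imputes missing or inconclusive readings as false results. If 5% of bleeding patients lacked a reading (an assumption), the chance falls to (0.99 x 0.95)^22 = 26%. How to form an interval in a sparse cell is ordinary SAP detail, and a plain exact binomial interval would ignore the centre intercept that the protocol specifies.

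**Conclusion.** The point holds as an error in a stated analysis rule. As written, the NPV part of EP5 cannot be computed from the model the protocol names, and its complement carries the name of a different quantity. At the planning values the correct NPV is 99.98% (99.99% to 99.96% over prevalence 0.6% to 4%). The 95% figure is conditional on an analyst using the primary model instead, and is not a consequence of the plan as written.

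The weight is small. EP5 is descriptive, carries no hypothesis and does not enter the sample size, and the PPV sentence shows what was meant. No primary conclusion changes. The conclusion about the wording rests only on the model as section 12.1.3 states it. The sizes rest on the planning values, a binary test and no centre effect.

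**What to change.** In section 12.1.3 and in the synopsis, replace the NPV sentence with one to this effect: *The false omission rate (1 - NPV) is obtained as the marginal mean of this model at a negative test result, and the NPV is reported as its complement.* This corrects both the conditioning and the label, and leaves the model and its random centre intercept as they are.

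Optionally, delete the p-values for the predictive values in the same two places, since reporting is descriptive and no null value is stated.

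The cost is one sentence in each of two places, and a check that the SAP says the same. No data collection, sample size or primary analysis is touched.

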12.1.4 Safety analysis

Safety analysis will be performed in the safety population, i.e. all patients enrolled (= all patients giving signed informed consent), irrespective of whether index thyroid surgery has been performed according to study protocol. Safety analysis will cover relevant aspects of safety reporting to regulatory bodies according to EU MDR Article 80.

12.1.5 Subgroup analysis

Subgroup analyses for primary and secondary endpoints are based on the same analysis sets and ITD scope as in the main analyses of these endpoints. The subgroup analyses are presented descriptively without formal hypotheses testing and will be performed post-hoc.

12.2 Sample Size and Power Calculations

Initial sample size calculation for the stage 1 study is performed for the first primary hypothesis considering sensitivity and specificity as co-primary endpoints. This hypothesis states the superiority considering sensitivity and specificity of the IP against pre-defined minimum thresholds. The optimal sample size calculation for a single-arm confirmatory diagnostic accuracy study is applied [28].

The sensitivity of the IP is assumed to be 99%, the specificity is assumed to be 95%. The pre-defined minimum sensitivity equals 80%, the minimum specificity is 65%. A higher minimum sensitivity than minimum specificity is chosen as false negative results are much more relevant for the patient than false positive results. The assumed prevalence of clinically relevant hemorrhage within 48 hours following thyroid surgery is 1.5%. The two-sided significance level is set to 5% for the endpoint considering sensitivity and the endpoint considering specificity, respectively. An overall power of 80% is aimed. This leads to a total sample size of 1,470 patients enrolled and measured which is based on the assumed prevalence of 1.5%. Due to the optimal sample size calculation, the endpoint considering the sensitivity reaches a power of 86% and the endpoint considering the specificity a power of 98%. If the prevalence differs at least 22 events of clinically relevant hemorrhage within 48 hours following thyroid surgery need to be observed. Consecutive patient recruitment without any selection is important to receive valid estimates of predictive values as secondary endpoints.

The sample size calculations are performed with R version 4.0.2.

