12.1.2 Analysis of the primary endpoint

Analyses of the co-primary endpoints in the stage 1 diagnostic study are based on the population of all enrolled patients with subsequent index thyroid surgery. This corresponds to the intention to diagnose (ITD) principle, whereas missing or inconclusive values are imputed by false positive or false negative results, respectively [25]. In accordance with the ICH E9 guidelines, the analysis population of all these patients is defined as the "Full Analysis Set" (FAS).

In the first pair of primary hypotheses, sensitivity and specificity are considered as co-primary endpoints. They are combined via the Intersection-Union Test. The global null hypothesis can only be rejected if both individual null hypotheses of sensitivity and specificity are rejected. The corresponding first global alternative hypothesis states that the IP exceeds a pre-defined minimum sensitivity of 80% and specificity of 65%. The second primary global hypotheses, the second primary global hypothesis can only be evaluated in a confirmative way if the first global primary hypothesis leads to a significant result. The hierarchical order of hypotheses requires no adjustment of the type I error rate.

The analysis of the first global primary hypothesis contains the estimation of the resulting sensitivity and specificity of the IP according to the defined cut-off value of 12 mmHg. For the estimation, a mixed binary logistic regression model is used [26]: The binary test result represents the dependent variable, the true disease status is included as fixed effect. Additionally, a random-intercept is estimated for each centre. Sensitivity is estimated via the calculation of the marginal mean for a diseased individual (=surgical intervention performed which confirmed post-operative hemorrhage needing intervention). False-positive rate, which is the counter probability of the specificity, is estimated via the calculation of the marginal mean for a non-diseased individual. Twosided 95%-logit confidence intervals with p-values are reported.

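### Section 12.2 and the synopsis state powers the design does not have: 98% for specificity fits about 22 patients rather than 1,448, 86% for sensitivity is an approximation that 22 events cannot deliver, and neither allows for readings imputed as errors

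*Protocol*

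**What the plan says.** Protocol section 12.2, repeated in the synopsis, sets the inputs. On expected performance it states: "The sensitivity of the IP is assumed to be 99%, the specificity is assumed to be 95"%. For the thresholds that the device has to beat, it states: "The pre-defined minimum sensitivity equals 80%, the minimum specificity is 65"%. On how often bleeding is expected, it states: "The assumed prevalence of clinically relevant hemorrhage within 48 hours following thyroid surgery is 1.5"%. On the error rate for each co-primary endpoint, it states: "The two-sided significance level is set to 5% for the endpoint considering sensitivity and the endpoint considering specificity, respectively". The target is worded as "An overall power of 80% is aimed". The result is given as "This leads to a total sample size of 1,470 patients enrolled and measured which is based on the assumed prevalence of 1.5"%, with at least 22 bleeds required if prevalence differs. The component powers follow: "the endpoint considering the sensitivity reaches a power of 86% and the endpoint considering the specificity a power of 98"%.

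Section 12.1.2 fixes how the same endpoints are analysed. Under the intention-to-diagnose principle, "missing or inconclusive values are imputed by false positive or false negative results, respectively". Sensitivity and specificity come from a mixed logistic model with a random intercept per centre and 95% logit intervals. Both lower limits must exceed their thresholds for success.

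Section 12.3 re-estimates the sample size at half recruitment from the observed prevalence, with a maximum of 4,500.

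**The concern.** Three things in the power statement look wrong.

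- Specificity is estimated in almost the whole cohort, and the gap between 95% and 65% is wide. A power as low as 98% is implausible with more than 1,400 patients.
- Sensitivity rests on about 22 patients with 0.01 × 22 = 0.22 misses expected. A formula that treats the number of misses as continuous is unreliable there.
- The assumed 99% enters the calculation unchanged, although the primary analysis counts an unusable reading in a bleeding patient as a miss.

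Sensitivity alone decides whether the trial has its 80% power. If the true figure has no margin, and technical failures lower it further, the sponsor and ethics committees are relying on a probability of success that the design does not offer.

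**Working it through.** **Inputs (section 12.2).** Sensitivity 0.99 against 0.80; specificity 0.95 against 0.65; two-sided 5%, so 0.025 in the direction tested; N = 1,470; prevalence 1.5%. Events: 1,470 × 0.015 = 22.05, taken as 22. Non-events: 1,470 − 22 = 1,448.

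**Step 1. Reproduce the stated figures.** One-sample normal approximation:

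power = Φ{[|p1 − p0|·√n − 1.96·√(p0(1 − p0))] / √(p1(1 − p1))}

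- Sensitivity, n = 22: (0.19 × 4.690 − 1.96 × 0.400)/0.0995 = 1.08, so 85.9%. The stated 86% reproduces.
- Specificity, n = 1,448: (0.30 × 38.05 − 1.96 × 0.477)/0.218 = 48.1, so essentially 100%. The stated 98% does not reproduce.
- Specificity, n = 22: (0.30 × 4.690 − 1.96 × 0.477)/0.218 = 2.17, so 98.5%. The exact binomial gives 97.8%.

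The number of events therefore appears to have served as the denominator for specificity. Using the same n for both endpoints, the product of the two powers is 0.791 at n = 21 and 0.846 at n = 22, which would explain why 22 was chosen. With the true number of non-events, 21 events (N = 21/0.015 = 1,400) already give 80.8% by this formula, so the error makes N about 5% larger than the formula needs.

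**Step 2. Sensitivity as a discrete test at 22 events.**

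| Result | Exact one-sided p against 0.80 | Clopper-Pearson lower limit | Score z | Rejects? |
|---|---|---|---|---|
| 22/22 | 0.8^22 = 0.0074 | 0.846 | 2.35 | yes |
| 21/22 | 0.048 | 0.772 | (0.9545 − 0.80)/√(0.16/22) = 1.81 | no |

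Under either test only 22/22 rejects, so power = 0.99^22 = 80.2%. With specificity at about 100%, overall power is also about 80%.

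**Step 3. The planned logit interval, ignoring centre effects.** Lower limit = expit{log(a/b) − 1.96·√(1/a + 1/b)}, with a the positives and b the misses.

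- 21/22: log 21 − 1.96·√(1/21 + 1) = 1.038, so 0.739.
- 22/22: undefined, because b = 0. With 0.5 added to each cell: log 45 − 1.96·√(1/22.5 + 2) = 1.004, so 0.732.

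Neither exceeds 0.80. Neither 86% nor 80.2% is the power of this rule.

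**Step 4. Worst-case imputation.** The protocol gives no failure rate, so the share m of bleeding patients without a valid reading is an assumption. Effective sensitivity = 0.99(1 − m).

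| m (assumed) | Effective sensitivity | Exact power | Normal approximation |
|---|---|---|---|
| 0% | 0.990 | 80.2% | 85.9% |
| 0.5% | 0.985 | 71.8% | 75.6% |
| 1% | 0.980 | 64.3% | 66.8% |
| 2% | 0.970 | 51.4% | 53.4% |
| 5% | 0.941 | 25.9% | 29.9% |

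By the normal approximation, power reaches 80% at m of about 0.28%. For specificity, 20% missing gives 0.95 × 0.80 = 0.76, and power at 1,448 is still about 100%.

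**The case against.** The best defence is that 86% is correct by a standard formula, that the specificity error only understates power, and that the exact figure still meets the 80% aimed for. All three points stand. Preferring an exact test is a choice of method, and the cited sizing method is not available to check. What remains is that 86% suggests a margin that a discrete result from 22 patients cannot provide, and that it does not correspond to the decision rule in section 12.1.2.

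A second defence is that the imputation losses are scenarios. Section 12.2 does not say whether 99% is already net of technical failure. Section 4.1 censors a shortened recording at its last measurement, so a patient who crossed 12 mmHg before the failure could still count as positive. Section 12.4 limits the full analysis set to patients whose monitoring was started, whereas section 12.1.2 takes all enrolled patients with index surgery, so how often imputation applies is unclear. These points bear on the size of m. They do not remove the need to state it, and section 4.1 itself foresees device problems and early sensor removal.

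Three stronger readings are tempting and are not supported.

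- A reader might infer that 0.86 × 0.98 = 0.84 contradicts 80%. It does not: 80% is a target, and the excess is what rounding up to a whole event produces (0.791 at 21, 0.846 at 22).
- A reader might infer that the power holds only if no reading is ever missing. Missing readings in patients without a bleed do practically no harm; only the roughly 22 events matter.
- A reader might infer that 22 of 22 is the protocol's success criterion, so that one failed sensor ends the trial. That criterion belongs to the exact and score tests. The protocol decides by a model-based logit interval, 22 is a minimum, and the sample may grow to 4,500.

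**Conclusion.** The point holds in three parts.

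1. The 98% for specificity is wrong for about 1,448 non-events; the power exceeds 99.9%. The error is conservative and threatens no conclusion.
2. The 86% for sensitivity is valid only as a normal approximation. The attainable power at exactly 22 events is 80.2% by an exact or score test, so overall power is about 80% with nothing in reserve. It is not the power of the planned logit interval. The limits of 0.739 and 0.732 ignore centre effects, and the mixed-model interval may differ from them.
3. The sizing contains no stated allowance for the imputation rule. Power falls to about 64-67%, 51-53% or 26-30% if 1%, 2% or 5% of bleeding patients lack a valid reading. These rates are assumptions, applied to a true sensitivity of 99% among valid readings. The prevalence-only re-estimation in section 12.3 would not detect or correct the loss.

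The third part has the largest consequence. It cannot be left to the SAP, because the sample size, the component powers and the imputation rule are all fixed in this protocol.

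**What to change.** In section 12.2 and the synopsis:

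- Restate the specificity power as above 99.9%, calculated from the number of non-events.
- Restate the sensitivity power at 22 events as about 80% (exact). Name the test it refers to, and make that test agree with the interval used for the decision in section 12.1.2, including what is done when no miss is observed.
- State an assumed rate of missing or inconclusive readings among bleeding patients, and give the resulting power under intention to diagnose.
- Use the corrected calculation for the re-estimation in section 12.3.

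The restatement costs an amendment to the text and a less favourable published power; it needs no extra patients. Aligning the test with the interval may mean amending the interval for sensitivity.

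More events are needed only if the sponsor wants to hold 80% at a non-zero failure rate. By the normal approximation that takes 30 events (N = 30/0.015 = 2,000) at 2% missing, 49 (N about 3,270) at 5%, and 133 (N about 8,870, above the 4,500 cap) at 10%. For information, under an exact test one miss becomes admissible at 26 events: 25/26 has a lower limit of 0.804, and power is 97.2% with nothing missing and about 82% at 2% missing.
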